6.3 PER-PROTOCOL POPULATION (PP)

The per-protocol population (PP) will include all mITT subjects who do not have a major protocol violation as described in section 7.4.

6.4 SAFETY POPULATION

The safety population includes all ITT subjects who underwent treatment. The safety population is the primary population for analyses of adverse events. Subjects are analyzed according to the treatment which they received, regardless of initial randomization.

7 GENERAL ISSUES FOR STATISTICAL ANALYSIS

Data will be presented using descriptive statistics. Categorical data will be presented using frequencies and percent of subjects in each category. Continuous data will be presented using mean, standard deviation, median, minimum, maximum, and sample size.

Results will be generated by treatment group.

7.1 ANALYSIS SOFTWARE

Analysis data sets, statistical analyses and associated output generated by Boston Biomedical Associates will be generated using SAS® Software version 9.4 or later.

7.2 DISPOSITION OF SUBJECTS AND WITHDRAWALS

A CONSORT diagram will be presented based on the ITT population. All subjects who provide written informed consent will be accounted for. The frequency of subjects who completed each scheduled assessment will be presented. The number and percentage of ITT subjects prematurely withdrawing will be presented overall and by reason of discontinuation in a table.

7.3 METHODS FOR WITHDRAWALS AND MISSING DATA

The primary endpoint analyses will be analyzed using all available data in the mITT population. An additional sensitivity analysis will be performed for the primary endpoints using last observation carried forward (LOCF) in the mITT population.

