6.8 Treatment compliance

A lack of compliance during the Screening Phase will result in an exclusion from the Active Phase of the study. Once treatment occurs, a subject can only be excluded from the study due to the following:

- 1. Withdrawal of consent
- 2. Lost- to follow-up
- 3. Death
- 4. Subject undergoes subsequent surgery on the treated disc
- 5. Investigator withdrawal due to subject's study compliance

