6.10 Subject Withdrawal and Replacement

Subjects may withdraw from the study at any time without penalty and for any reason without prejudice to their future medical care. In all cases, the reason(s) for withdrawal, and the primary reason, must be recorded on the appropriate case report form (CRF). If a subject is prematurely withdrawn from the study after randomization (Day 0 of the Active Phase), the investigator must document the reason(s) and make every effort to perform a final Termination Visit. The procedures to be followed for the Termination Visit are the same as those defined for the Month 12 Visit.

Subjects that are consented, screened and randomized, but do not undergo a successful transplantation (Day 0 of the Active Phase) will be considered screen failures. These randomization assignments will be re-used. The randomization and the replacement of subjects will be orchestrated through a 3rd party designated independent of the data collection or analysis.

CONFIDENTIAL	Clinical Protocol	DATE	Р	age
		9Dec2019		
Patients with Low Back Pain with	mented Disc Regeneration in the $\underline{\mathbf{T}}$ reatment of th or without Intervertebral Disc Herniation –	WRITER TG, DB, PW	NO. 29	REV 6
VAST-001-017				

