8.4.1 Transplant of supplemental allograft into the affected disc

All subjects randomized to active allograft will undergo an intervertebral lumbar injection into the target disc. The procedure of injecting the intervertebral disc will involve placing a 22-gauge needle into the center of the affected intervertebral disc. No contrast will be used prior to the injection of the supplemental allograft and 1mL of cells (approximately 6*10⁶ cells) mixed in a 1:1:0.75 by-volume ratio (Cells in cryoprotectant: Saline: NP) will be injected into the center of the affected disc(s) in the location of the nucleus pulposus. At least 1.5-2 milliliters of the resulting mixture will be available for injection into the nucleus pulposus of the symptomatic disc. Volume injected will be recorded.

Vital signs will be recorded prior to injection. The treatment injection should be carefully controlled. The injection procedure MUST be stopped if any of the following occur:

- The investigator cannot accurately place the needle tip in the nucleus pulposus
- The subject becomes hemo-dynamically unstable during the injection procedure.

CONFIDENTIAL	Clinical Protocol	DATE	P	age
		9Dec2019		T
TITLE: V iable A llograft S upplemented Disc Regeneration in the T reatment of		WRITER	NO.	REV
Patients with Low Back Pain wit	th or without Intervertebral Disc Herniation –	TG, DB, PW	36	6
VAST-001-017				

The following information regarding the treatment procedure must be documented:

- Procedure start and stop time
- Treatment administration stop time
- Treatment interruption information, if applicable
- Total volume of treatment injected
- Pain on implantation
- Anesthesia type(s)

The information collected above will also be collected during the placebo cross over visit.

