	mented Disc Regeneration in the $\underline{\mathbf{T}}$ reatment of th or without Intervertebral Disc Herniation –	WRITER TG, DB, PW	NO. 38	REV 6

- MRI evaluating the intervertebral height, adjacent endplates, deprivation of fluid and Pfirrmann score will be obtained during the Screening Phase and in the 2 weeks prior to transplant, and in the Active Phase at 12 months. Subjects will be randomized, yes or no (1:1 ratio), to receive an MRI at 6 months. Conservative care subjects that crossover to the allograft treatment group will all receive an MRI at 6-month follow-up after allograft treatment.
- X-rays will be performed static (standing), anterior-posterior and lateral in the Screening Phase prior to transplant. After transplantation, during the Active Phase (Months 6, and 12) a static and an additional dynamic (flexion/extension) X-rays will be performed.
- Adverse Events (AEs) and Serious Adverse Events (SAEs) will be recorded once the
 patient is enrolled (Day 0 of the Active Phase). A detailed discussion of AEs and SAEs is
 located in Section 14. Optional checkup evaluations will be performed in the case of
 complications. Failure of treatment defined as the necessity of a follow-up operation
 will be documented separately.
- Laboratory investigation will be conducted according to the routine procedures of each investigational center. The valid normal ranges including the methods for all parameters will be provided to the sponsor prior to the start of the study. Only laboratory values outside the normal range will be evaluated and commented upon by the investigator. The following parameters will be determined:

Hematology: Clinical Chemistry:

- hemoglobin - creatinine

- hematocrit - alkaline phosphatase

- erythrocytes - AST/SGOT - leukocytes - ALT/GPT - thrombocytes - γ -GT

- erythrocyte sedimentation rate - glucose

Coagulation:

- PTT

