3.2.2 SECONDARY ENDPOINTS

The study's secondary endpoints are:

- Improvement in ODI and VASPI at 6 months after treatment
- Improvement in the SF-36 at 6 and 12 months after treatment
- MRI measurements at 6 and 12 months after treatment
- Adverse Event (AE)/ Serious Adverse Events (SAE) rates after treatment
- Hospitalization rate at 12 months after treatment
- Re-operation rate at 12 months after treatment
- Resource utilization following treatment at 6 and 12 months after treatment
- Changes in laboratory tests

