11.2 Responder Analyses

A responder analysis will be performed for both primary endpoints. For the ODI, a subject with at least a 15-point reduction will be considered a responder. For the VAS, a subject with at least a 50% reduction will be considered a responder. The chi-square test of independence will be used to compare the percent of subjects considered a responder in each treatment group.

Additionally, regressions will be used to determine whether any characteristics are associated with responder status.

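### The responder analysis has no rule for re-operated subjects, and eligible randomised subjects without a successful injection enter no efficacy analysis

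*SAP*

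**What the plan says.** **Re-operation.** Protocol 6.8 lists the only grounds on which a treated subject can be excluded; one is "Subject undergoes subsequent surgery on the treated disc". Protocol 8.5 has a separate recording rule: "Failure of treatment defined as the necessity of a follow-up operation" is to be documented. Protocol 6.10 asks for every effort at a Termination Visit with the Month 12 procedures.

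For the primary endpoints SAP 7.3 says "The primary endpoint analyses will be analyzed using all available data in the mITT population", with LOCF in mITT as a sensitivity analysis. SAP 11.2 gives the responder cut-offs, for example "For the ODI, a subject with at least a 15-point reduction will be considered a responder", and a chi-square test. It names no population and does not mention missing or re-operated subjects. Elsewhere the event appears as a secondary endpoint, "Re-operation rate at 12 months after treatment", which SAP 9.2 compares between arms. Withdrawals are tabulated under SAP 7.2: "The number and percentage of ITT subjects prematurely withdrawing will be presented overall and by reason of discontinuation in a table".

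**Unsuccessful injection.** Under Protocol 6.10, subjects who are consented, screened and randomised but not successfully transplanted become screen failures, and "These randomization assignments will be re-used". SAP 6.2 restricts mITT to ITT subjects who underwent treatment and have a post-treatment ODI and VASPI. SAP 6.3 makes PP a subset of mITT, and SAP 9 runs efficacy only in those two sets. SAP 6.1 defines ITT as all enrolled subjects, with enrolment at confirmed eligibility, as in Protocol 16. Protocol 6.2 instead places enrolment at successful treatment.

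**The concern.** The protocol calls one event a treatment failure, yet the responder analysis has no rule that makes it one. A re-operated subject who leaves may be missing and drop out of the denominator. One who stays may supply a Month 12 score improved by the surgery and count as a responder. Two analysts could follow the SAP and report different rates. SAP 7.3 also does not say whether a Termination Visit score taken before Month 12 is 12-month data, which affects the available-case analysis as well.

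The second part concerns removal after randomisation. A failed injection can arise only in the two injection arms; conservative care has no counterpart. If the removed subjects would have done worse or better than average, the contrast with conservative care is biased, and no planned efficacy analysis would show by how much.

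**Working it through.** **Inputs.** The documents give no re-operation, dropout or failed-injection rate, so there is no plan figure to reproduce on this point. From SAP 4: SD 15.5, relevant difference 9 points, arms 140/40/40. The SAP's probability follows from these inputs: Φ(−9/(15.5·√2)) = 0.3407, against 0.341 stated. Everything else below is assumed.

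**1a. Responder rate, direct arithmetic.** Suppose 14 of 140 allograft subjects are re-operated and 63 of the other 126 respond.
- Dropped: 63/126 = 50%.
- Non-responders: 63/140 = 45%.
- All 14 counted as responders on post-surgery scores: (63 + 14)/140 = 55%.

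**1b. Difference between arms, no true effect.** Assume mean improvement 10 in both arms, SD 15.5, and re-operated subjects drawn from the worst outcomes. P(improvement ≥ 15) = 1 − Φ((15 − 10)/15.5) = 0.3735. With re-operation in 10% of allograft and 5% of placebo:
- Non-responders: difference 0.
- Dropped: 0.3735/0.90 − 0.3735/0.95 = 0.415 − 0.393 = +2.2 percentage points.
- Post-surgery scores counted as response: (0.3735 + 0.10) − (0.3735 + 0.05) = +5.0 percentage points.

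With equal rates all three differences are 0. With 5% on allograft and 10% on placebo the last two become −2.2 and −5.0.

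**1c. Available-case analysis under the SAP success rule.** If 10% of an arm exits, its mean ODI improvement shifts by ρ·φ(1.2816)/0.90 × 15.5 = 3.02, 1.51 and 0 points for exit–outcome correlation ρ = 1, 0.5 and 0. Simulated 140/40/40 trials used normal scores, no true effect and 16,000 trials per cell, with exit linked to ODI improvement. The table gives the percentage of trials with both Kruskal-Wallis tests at p < 0.05.

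| Exits, allograft/placebo/conservative | ρ | ODI–VASPI correlation 0.3 / 0.5 / 0.7 |
|---|---|---|
| none | – | 0.4 / 0.9 / 1.4 |
| 10/10/10% | all | 0.3 to 1.6 |
| 10/5/5% | 0.5 | 0.5 / 0.9 / 1.5 |
| 10/5/5% | 1 | 0.8 / 1.2 / 2.3 |
| 10/0/0% | 0.5 | 0.8 / 1.5 / 2.6 |
| 10/0/0% | 1 | 1.8 / 3.7 / 6.6 |

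If exit instead follows the sum of ODI and VASPI, the 10/0/0% rows become 0.9 / 1.5 / 3.1 at ρ = 0.5 and 3.1 / 4.9 / 8.2 at ρ = 1.

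**2. Unsuccessful injections.** If a fraction f of injections fails and the others improve by m on average, scoring failures as no change lowers the arm mean from m to (1 − f)·m, a shift of f·m:
- f = 2%, m = 10: 0.2 points.
- f = 5%, m = 15: 0.75 points.
- f = 10%, m = 20: 2.0 points.

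On 140 + 40 = 180 injection-arm places, 2%, 5% and 10% are about 4, 9 and 18 subjects.

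**The case against.** **Safeguards exist.** Re-operation rates are tested between arms, withdrawals are tabulated by reason, and LOCF may pick up a Termination Visit or Month 6 score. The responder analysis lies outside the success rule in SAP 7.5 and 9.1. All of this is correct. It makes the event visible and softens the effect on the primary endpoints, but it does not score the event in the responder analysis.

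**A reader might infer that re-operated subjects are always dropped.** Protocol 6.8 permits exclusion and does not require it. The gap is the missing rule, which leaves both routes open.

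**A reader might infer that the trial's false-positive rate is badly inflated.** A single allograft-versus-placebo rank test with worst-outcome exits rejects in 9.5% of null trials at 10% against 5% exits, and in 19.5% at 15% against 5%. That is not the SAP's rule, which needs two significant Kruskal-Wallis tests. Under that rule 5% is passed only in the most extreme cells.

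**A reader might infer that every stopped injection is excluded.** Protocol 8.4.1 gives reasons to stop, such as "The investigator cannot accurately place the needle tip in the nucleus pulposus", but nothing equates a stopped injection with an unsuccessful transplantation. Interruption and volume delivered are recorded, and mITT requires only that treatment was undergone, so a partly delivered injection may count as treated. Some cases may also be true eligibility failures: Protocol 8.1 requires disc confirmation and the ability to undergo transplantation, and Protocol 7.1.2 requires the criteria still to be met at Day 0. The number affected may be small.

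**A reader might infer that the allograft–placebo contrast is compromised, or that ITT is undefined.** Both injection arms share the procedure, and nothing shows unequal failure between them. SAP 6.1 governs the analysis set; Protocol 6.2 is a wording conflict to be tidied.

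**Conclusion.** Both parts hold on the text. First, an event that the protocol records as treatment failure can leave the responder denominator or count as a response. In the worked case the rate is 45%, 50% or 55% according to a choice the SAP does not make. Second, randomised subjects with confirmed eligibility but no successful injection reach no efficacy analysis, so the contrast with conservative care is not fully as randomised.

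Severity is low to moderate. With 10% exits on allograft only and exit–outcome correlation 0.5, false success under the SAP rule is about 0.8 to 2.6% (up to 3.1% if exit follows both scores), against 0.4 to 1.4% with no exits. Bias can run in either direction, and equal exits cause no material inflation. Part two moves an injection-arm mean by about 0.2 to 2.0 points, against the plan's 9-point relevant difference. All rates, correlations and mean improvements are assumptions.

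**What to change.** - **SAP 11.2:** count subjects with surgery on the studied disc before Month 12 as non-responders, in all three arms.
- **SAP 7.3:** state whether a Termination Visit score taken before Month 12 counts as 12-month data.
- **SAP 9:** add an efficacy sensitivity analysis of all randomised, eligibility-confirmed subjects as randomised, on the SAP 6.1 ITT definition. State the imputation where no follow-up score exists, for example no change. Report these subjects by arm.
- **Protocol 6.10:** keep these subjects in ITT and, if enrolment is still open, stop re-using their assignments.
- **Protocol 6.2:** align the enrolment wording with Protocol 16 and SAP 6.1.

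The primary analysis stays as it is. A worst-rank analysis of re-operated subjects is optional and not part of the fix. It targets a different estimand. With identical scores and purely random exits of 3/10/10%, it makes both Kruskal-Wallis tests significant in 3.2 to 6.0% of simulated trials.

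The cost is two small additions to the analysis, some wording, and possibly a less favourable responder rate. No-change scoring is a single imputation and is conservative for the injection arms, so it belongs in a sensitivity analysis.

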7.1.4 Conservative Treatment Group 3 Months (± 14 days), or VA3

Patients randomized to the conservative arm will be evaluated with VASPI, ODI, SF-36 questionnaires as well as complete all required additional assessments as outlined in Appendix A during the 3 months visit. Patients will be evaluated for deteriorating or improving conditions relative to enrollment. Subjects who have experienced a significant decline in condition defined as a 10% increase in pain by VASPI, or a 9-point increase in ODI will be offered the allograft treatment as a crossover. If the subject does not meet the aforementioned changes in ODI or VASPI, or is considering withdrawal, they may also be offered the allograft treatment by physician discretion if condition has significantly declined. Subjects that crossover do not have to re-consent. The crossover allograft treatment can occur at any time period after the 3-month follow-up visit. To administer the crossover allograft treatment, a new visit will be scheduled and this visit will be considered as the new Active Phase Day 0. In addition to the 3 months follow-up visit assessments, these crossover subjects will receive a MRI and X-ray prior to the allograft treatment. All assessments done at this 3 months follow-up visit will be considered as the new baseline assessments. These crossover subjects will receive follow-up visits at 6 months and 12 months after allograft treatment. Crossover subjects will not be replaced by enrolling new patients in the conservative care treatment group.

7.1.5 Active Phase Month 6 (± 30 days) or VA4:

All randomized subjects will return to the clinic 6 months (± 30 days) subsequent to treatment for all safety and efficacy assessments as outlined in Appendix A. ODI, VASPI, and SF-36 questionnaires will be completed by the subject, and assisted by physician or physician designee. All subjects (excluding conservative care crossover subjects) will be randomized to include MRI at 6-month (MRI or no MRI, ratio 1:1) follow-up in addition to all other assessments. This randomization is performed to assess whether predictability at 6 months indicates performance at 12 months. The conservative care subjects that crossover to the allograft treatment group will all receive an MRI at 6-month follow-up after allograft treatment. All subjects will receive an X-ray at the 6-month follow-up visit. Additionally, a review of resource utilization since the Day 0 visit will be completed.

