APPENDIX A - STUDY SCHEDULE

Visit	VS1 ^a	VA1 ^a	VA2 ^b	VA3 ^c	VA4	VA5	VA6	VA7
Visit Window	Screening (Day -14 to 0)	Day 0	1 month (±3 Days)	3 months (±14 Days)	6 months (± 30 Days)	12 months (+ 30 Days)	24 months (± 3 Months)	36 months (± 3 Months)
Informed Consent	Х						Х	
Eligibility Criteria	Х							
Eligibility Criteria Check		Х					х	
Randomization		Х						
Injection Treatment (Allograft or Saline)		Х					X ^f	
Demographic Data	х							
Medical History	х							
Physical Examination		Х	х	Х	Х	Х	X ^f	
Neurological Examination		Х	Х	X	X	X	Χ ^f	
MRI and X-ray Evaluations	X		X	X ^d	X e	X	X ^f	
Laboratory Investigation	Х		Х	Х	Х	Х	X ^f	
Urine/Pregnancy Test, if applicable		Х						
VASPI Questionnaire	х		х	Х	х	х	х	Х
SF-36 Questionnaire	x		х	х	х	х	х	x
ODI Questionnaire	х		х	Х	х	х	х	х
Resource Utilization	Х				Х	Х	Х	Х
Concomitant Medication	Х	Х	Х	Х	Х	Х	Х	Х
Adverse Events		Х	х	Х	Х	Х	Х	Х

^a VS1 and VA1 may both occur on Day 0.

^b Month 1 Visit (VA2*) to be performed for the first 24 subjects randomized only.

CONFIDENTIAL	Clinical Protocol	DATE 9Dec2019	Pa	ige
	mented Disc Regeneration in the $\underline{\mathbf{T}}$ reatment of th or without Intervertebral Disc Herniation –	WRITER TG, DB, PW	NO. 57	REV 6

^c Subjects randomized to conservative care will be evaluated at 3 months to assure they are not experiencing further debilitating changes. During this visit, subjects may be offered crossover to allograft treatment. To administer the crossover allograft treatment, a new visit will be scheduled and this visit will be considered as the new Active Phase Day 0 (VA1).

^d MRI and X-ray to be done in the event a subject crosses over from conservative care to the Allograft treatment.

^e At the 6-month follow-up visit, subjects will be randomized to receive a MRI, (1:1 ratio). Crossover subjects to allograft treatment will all receive an MRI at the 6 month visit after allograft treatment. All subjects will receive an X-ray at the 6 month follow up visit.

f At the 24-month in-office visit, subjects will first be reevaluated for inclusion/exclusion and fill out VASPI, ODI, SF-36, and Resource Utilization. If eligible for allograft treatment, the PI will perform a neurological exam, physical exam, laboratory investigation, and MRI/X-ray.

[figure not shown]
CONFIDENTIAL	Clinical Protocol DATE		Page	
99111 12 E111111 12		9Dec2019		

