6.2 MODIFIED INTENT TO TREAT POPULATION (MITT)

The modified intent-to-treat population (mITT) includes all ITT subjects who underwent treatment and had at least one valid post-treatment assessment of the ODI and VASPI. This mITT population is the primary analysis population for efficacy analyses. Subjects are analyzed under the treatment to which they were randomized.

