9 EFFICACY ANALYSES

The co-primary efficacy variables will be analyzed in the mITT population (primary) and repeated in the PP population (sensitivity). The secondary variables will be analyzed in the mITT and PP populations.

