11 OTHER PLANNED ANALYSES

11.1 PRIMARY ANALYSIS ACCORDING TO TREATMENT RECEIVED

A sensitivity analysis will be performed for the primary endpoints according to treatment subjects received, regardless of their initial randomization.

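### LOCF is the only missing-data check, and because a Month 3 score is scheduled only under conservative care it can fill the arms from different times, with a bias whose direction the plan leaves open

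*SAP*

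**What the plan says.** SAP 7.3 sets the primary approach: "The primary endpoint analyses will be analyzed using all available data in the mITT population". It then adds the single missing-data check: "An additional sensitivity analysis will be performed for the primary endpoints using last observation carried forward (LOCF) in the mITT population". SAP 13 records that LOCF, which Protocol 13.2.1 names for the ITT and PP analyses, was moved to this supporting role. Neither document says which visits may be carried forward. The other two sensitivity analyses, per-protocol (SAP 9) and as-treated (SAP 11.1), change who is analysed or under which label. Neither fills in a missing score.

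To enter mITT, a treated subject must have "had at least one valid post-treatment assessment of the ODI and VASPI" (SAP 6.2). Subjects are analysed as randomised.

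Post-treatment ODI and VASPI are scheduled as follows (Protocol 7.1.3 to 7.1.6, Appendix A):

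- Month 1: a visit "to be performed for the first 24 subjects randomized only", with at least four subjects from each arm.
- Month 3: "Patients randomized to the conservative arm will be evaluated with VASPI, ODI, SF-36 questionnaires". No other arm has this visit.
- Month 6: "All randomized subjects will return to the clinic 6 months (± 30 days) subsequent to treatment".
- Month 12: all arms.
- Early withdrawal: Protocol 6.10 asks sites to try for a termination visit with Month 12 procedures, whatever the arm.

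Under Protocol 7.1.4, conservative subjects who have worsened at Month 3 (ODI up 9 points, VASPI up 10%, or on physician judgement) may cross over to allograft, and the Month 3 scores become their new baseline. Neither document says whether post-crossover scores count as Month 12 data for the randomised arm, or from which baseline change is then measured.

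**The concern.** A missing-data sensitivity analysis should show whether the primary result survives a different but reasonable assumption about the subjects without a Month 12 score. LOCF does this poorly here, for three reasons.

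- The last score before an early loss can be a Month 3 score in one arm and nothing at all in the other two.
- The Month 3 visit is also where worsened conservative subjects are identified, so the scores carried from it may be a selected set.
- LOCF replaces one fixed assumption by another and never asks how bad the missing scores would have to be to overturn the result.

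If LOCF agreed with the primary analysis, readers would take that as evidence of robustness. The agreement would partly reflect a visit schedule that differs by arm.

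**Working it through.** **Step 1: who can be carried.** The injected arms hold 140 + 40 = 180 subjects. At least 4 of the first 24 are conservative, so at most 24 − 4 = 20 injected subjects have a Month 1 score. At least 180 − 20 = 160 of 180 (89%) have no scheduled score before Month 6. All 40 conservative subjects have a scheduled Month 3 score.

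| Lost, with no termination visit | Conservative | Injected, outside first 24 |
|---|---|---|
| Between Months 3 and 6 | In mITT; Month 3 carried in LOCF | No score; not in mITT; in neither analysis |
| Between Months 6 and 12 | Month 6 carried | Month 6 carried |

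**Step 2: size of the shift.** The plan gives no figure for dropout, crossover or LOCF bias, so there is none of its own to reproduce. From SAP 4: SD 15.5 and target difference 9 points. These return the SAP's stated probability, Φ(−9/(15.5 × √2)) = 0.341. Assumptions:

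- no true Month 12 difference between arms;
- Month 3 to Month 12 correlation ρ = 0.6;
- SD 15.5 at both times;
- injected arms complete;
- a fraction f of the conservative arm carried from Month 3.

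A positive shift favours allograft.

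- *Carried at random, Month 3 mean d points worse than Month 12:* shift = f × d. For d = 5: 0.1 × 5 = 0.5, 0.2 × 5 = 1.0, 0.3 × 5 = 1.5. For d = 0 it is zero. For d = −5 the signs reverse.
- *Only the worst f at Month 3 carried:* shift = (1 − ρ) × SD × φ(z), with z the upper f point of the standard normal and φ its density. Here (1 − ρ) × SD = 0.4 × 15.5 = 6.2, so 6.2 × 0.1755 = 1.1, 6.2 × 0.2800 = 1.7 and 6.2 × 0.3477 = 2.2.
- *Everyone whose ODI rose by 9 or more carried (post-crossover scores treated as missing):* z = 9/15.5 = 0.581, about 28% of the arm; 6.2 × 0.3371 = 2.1.

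Simulation with 140/40/40 subjects and 3,000 runs per case:

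| Case | f = 10% | 20% | 30% |
|---|---|---|---|
| Random, equal means: shift (Kruskal-Wallis error) | 0.0 (5.6%) | 0.0 (5.7%) | 0.0 (4.6%) |
| Random, Month 3 worse by 5 | +0.5 (5.1%) | +1.0 (5.7%) | +1.5 (7.0%) |
| Random, Month 3 better by 5 | −0.5 (5.0%) | −1.0 (5.7%) | −1.5 (6.7%) |
| Worst f at Month 3 | +1.1 (5.8%) | +1.7 (8.1%) | +2.1 (9.9%) |

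Carrying every subject with a 9-point rise gave +2.1 points and 10.1% error (12.5% for the unadjusted allograft versus conservative Wilcoxon test). The simulation error on a 5% rate is √(0.05 × 0.95/3000) = 0.4 percentage points, so 5.8% is not clearly above nominal; 8.1% and higher are.

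For scale, 1.1/9 = 12% and 2.1/9 = 23% of the target difference. The standard error of the allograft versus conservative mean difference is 15.5 × √(1/140 + 1/40) = 2.8 points, so a 2.1-point shift is about three quarters of one standard error.

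**Step 3: post-crossover scores.** If they are kept under the randomised arm, Month 3 is not the last score and the 9-point-rise case does not arise. If they are kept but measured from the worsened Month 3 baseline, later improvement is credited to conservative care. If they are set to missing, LOCF reverts to the worsened Month 3 score. The plan does not choose.

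**Step 4: which comparisons.** Neither allograft nor placebo has a Month 3 visit, so that pair is untouched by it. The LOCF version of the three-group Kruskal-Wallis test can still move, because the conservative arm is in it.

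**The case against.** The strongest reply is that nothing in SAP 7.3 names Month 3. A Month 6 or termination-visit score supersedes it in every arm, so Month 3 is carried only for losses between Months 3 and 6 that have no exit visit. That is correct and limits the number affected. It does not remove the problem: the termination visit is only to be attempted, Protocol 6.8 expects loss to follow-up, and an unrestricted LOCF uses the last score there is.

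A reader might infer that LOCF here is built to favour allograft. The documents do not support that. The direction turns on how Month 3 compares with Month 12 and on the unwritten crossover rule, and nothing in the documents shows that conservative subjects who leave are those who declined. Allograft subjects lost after Month 6 also carry an earlier score, which works against allograft if improvement is still under way.

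A reader might also infer a shift of up to 0.2 × (9 + 9) = 3.6 points, 40% of the target. That needs 20% of the conservative arm lost in the Month 3 to 6 window without an exit visit, each worse by 9 points (the threshold at which crossover is offered), while every arm would otherwise improve by 9. The last figure turns a between-group target into a within-arm change. It is a corner case.

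Against imputation, it can be said that it too would draw on Month 3 in one arm only. That is true, but there Month 3 serves as a predictor of Month 12 rather than standing in for it, and subjects with baseline scores alone carry correspondingly more uncertainty.

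**Conclusion.** The concern holds in a limited form. LOCF in mITT is the only missing-data check. It can fill the conservative arm from Month 3 and the injected arms only from Month 6 or an exit visit (or Month 1 for a few), and it leaves out injected subjects lost before any score. The resulting bias in allograft versus conservative care is about 1-2 ODI points towards allograft if the worst 10-30% of Month 3 scores are carried, near zero if scores are carried at random with equal means, and the other way if Month 3 is better than Month 12. These figures rest on assumed dropout and correlation and apply to ODI; the documents give no SD for VASPI.

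It would be too strong to say that LOCF does not test the primary result at all, since it restores subjects who have a Month 6 but no Month 12 score. What it does not test is departure from missing at random. Trial success rests on the available-data Kruskal-Wallis tests (SAP 9.1), which this leaves unchanged. This is a cheap improvement to a supporting analysis.

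**What to change.** In SAP 7.3:

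1. Replace LOCF as the main missing-data sensitivity analysis with multiple imputation by randomised arm, from baseline and observed ODI and VASPI scores. Include all treated randomised subjects, also those with no post-treatment score.
2. Apply the same rank tests to each completed data set and state in advance how the Kruskal-Wallis and pairwise results are pooled across imputations.
3. Add a delta-adjusted tipping-point run that worsens imputed allograft scores in 3-point steps until significance is lost. Read it on the pairwise allograft comparisons, because Kruskal-Wallis has no direction. VASPI needs a step on its own scale.
4. State one rule for post-crossover scores: kept as randomised and measured from the study-entry baseline, or set to missing and imputed.
5. If LOCF stays as a further check, carry only Month 6 or termination-visit scores, which the protocol provides for in every arm.

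No new data collection is needed. The cost is SAP wording, modest programming (pooling rank tests is the least routine part) and a result that may be less favourable.
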